1.0 Objectives

1.1 Study Objectives

The primary aim is to determine whether breast cancer patients can be enrolled, randomized, retained, and comply with 6 months of aerobic exercise training; and, the feasibility of acquiring, managing and analyzing the cardiopulmonary fitness, cardiac function, quality of life, and tumor response data.

The secondary aim is to compare changes in hematological parameters (clinical blood biomarkers), cardiopulmonary fitness (VO₂max - stress testing), cardiac function (LVEF - echocardiogram), quality of life (surveys), and tumor response (tissue blocks from biopsy and surgical resection, MRI) in exercisers vs. control.

1.2 Primary Study Endpoints

Study completion - feasibility

1.3 Secondary Study Endpoints

n/a

2.0 Background

2.1 Scientific Background and Gaps

Several national and international agencies recommend exercise participation for all persons following a cancer diagnosis (1-3). The current evidence suggests that aerobic exercise training is safe during primary adjuvant therapy and improves cardiopulmonary function and patient related outcomes (1, 4). The vast majority of the studies in the meta-analyses that inform the recommendations and evidence base utilize standard prescription guidelines (50-75% of baseline exercise capacity for 12-15 weeks). Yet, aerobic exercise training prescriptions incorporating high-intensity exercise (85-95% of baseline heart rate peak) elicits superior improvements in exercise capacity compared with standard moderate intensity exercise prescriptions (5-7).

Few studies have tested the efficacy of exercise prescriptions that incorporate high intensity aerobic exercise training in cancer patients, especially those receiving chemotherapy (8-10). Hornsby et al. conducted a randomized phase II trial of 20 women with operable breast cancer initiating anthracycline containing neoadjuvant chemotherapy (11). They utilized a supervised moderate-to-high intensity aerobic exercise training program (60-100% VO₂max, 3 days per week) and observed 82% attendance to the supervised sessions and 66% adherence to the exercise prescription. Following assessment of adverse events during stress testing, during aerobic exercise training, clinician reported events (e.g. pain, nausea), and hematological parameters, they found that moderate-to-high intensity aerobic training with one-on-one supervision was safe. This is in line with Rao et al. whom demonstrated feasibility of a bootcamp intervention for 10 women with operable breast cancer initiating anthracycline containing neoadjuvant chemotherapy (12).

2.2 Previous Data

Evidence indicates that aerobic exercise training in breast cancer patients receiving chemotherapy is safe (8, 11, 13-22). It also appears to be efficacious. Hornsby et al demonstrated an increase in cardiopulmonary fitness of 13.3% in the intervention group (11). Cardiopulmonary fitness is highly predictive of overall and cardiovascular specific mortality in women (23-25). Specifically, an increase in cardiopulmonary fitness of approximately 10% has been associated with a 19% reduction in risk for CV mortality (26). This is important as breast cancer patients already present at diagnosis with 31% lower cardiopulmonary fitness levels compared to healthy age-matched women (27). This enhanced risk for

cardiovascular mortality in breast cancer patients is further compounded by cardiotoxic chemotherapy, which causes permanent cardiac damage (28).

It appears that aerobic exercise training is also beneficial for cancer outcomes, as pre-clinical work has shown enhanced tumor response when chemotherapy is combined with aerobic exercise training (29, 30). Clinically, in the same study population as the Hornsby et al study, Jones et al observed changes in circulating endothelial progenitor cells, cytokines, and angiogenic factors (31). Lastly, though underpowered to show significant differences, Rao et al reported smaller tumor sizes and lower Ki-67 scores for the bootcamp intervention group compared to controls (12).

2.3 Study Rationale

We seek to conduct an at home aerobic exercise training intervention in breast cancer patients whom elect to undergo neoadjuvant chemotherapy. We have previously conducted a similar at home aerobic training program for a national cohort of women at risk for breast cancer (32). Utilizing well monitored home based methods for exercise interventions decreases selection bias at enrollment as the intervention is not restricted to women with available resources to attend supervised exercise sessions. Home based exercise programming has similar adherence rates to supervised exercise programming (33). Further, home based exercise programming is more amenable to dissemination than supervised exercise training.

3.0 Inclusion and Exclusion Criteria

3.1 Inclusion Criteria

- Women with a breast cancer diagnosis (Stage I-IIIc)
- Sedentary (< 75 min/wk of moderate intensity exercise over the past month)
- No previous history of anthracycline based chemotherapy
- Absence of heart disease (clinical diagnosis of coronary artery disease, arrhythmias, congenital heart defects, dilated cardiomyopathy, or valvular heart disease)
- Absence of contraindications for neoadjuvant chemotherapy
- Scheduled to receive neoadjuvant chemotherapy
- Primary attending oncologist approval

3.2 Exclusion Criteria

- Absolute contraindications for exercise stress testing
 - acute myocardial infarction (3-5 days)
 - unstable angina
 - uncontrolled arrhythmias causing symptoms or hemodynamic compromise
 - syncope
 - acute endocarditis
 - acute myocarditis or pericarditis
 - uncontrolled heart failure
 - acute pulmonary embolus or pulmonary infarction
 - thrombosis of lower extremities
 - suspected dissecting aneurysm
 - uncontrolled asthma
 - pulmonary edema
 - room air desaturation at rest $\leq 85\%$
 - respiratory failure
 - acute noncardiopulmonary disorder that may affect exercise performance or be aggravated by exercise
 - mental impairment leading to inability to cooperate
 - decisional impairment
- Non-English speaking
- Women only diagnosed with ductal carcinoma in situ

- Women diagnosed with stage 4 metastatic breast cancer
- Pregnant women
- Men
- Children

3.3 Early Withdrawal of Subjects

3.3.1 Criteria for removal from study

Subject consent withdrawal

Development of contraindication to exercise testing or training

Subject is imprisoned, committed to a mental hospital, hospitalized for long term care, admitted to a drug/alcohol residential program, a residential living facility or alike.

3.3.2 Follow-up for withdrawn subjects

No follow up for withdrawn subjects

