5.3.2.1 Capability of Providing Consent

This will be determined by the oncologist.

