8.2 Sample size determination

N=10 intervention
N=10 control

Our intervention protocol is adapted from Hornsby et al. They report a final VO₂ of 1.6 ± 0.35 L/min in the intervention group and 1.2 ± 0.23 L/min in the control group. Thus, we are powered at 80% to see the same difference in VO₂ with 10 people per group assuming unequal variances. We have powered off of VO₂ as it is our physiological measure of intervention success per physiological adaptation.

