8.3 Statistical methods

Fisher's exact tests and χ^2 -tests will be used to examine between group differences in the overall proportion of patients experiencing treatment-related and training-related adverse events. A mixed-model repeated measures analysis of variance will be used to compare between group differences over time for outcome variables related to: cardiopulmonary fitness (VO₂max - stress testing), cardiac function (LVEF - echocardiogram), and tumor response (MRI). All efficacy outcomes will be assessed under the intention to treat principle. A two-sided significance level of 0.05 will be used for all statistical tests.

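### A woman removed for a medical contraindication to exercise gets no further follow-up, so obtainable secondary and safety data are lost for a health reason, and the mixed model's missing-data assumption is not stated

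*Combined protocol and SAP*

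**What the plan says.** Section 3.3.1 lists, among the criteria for removal from the study, "Development of contraindication to exercise testing or training". It does not distinguish between arms, or between stopping exercise and leaving the study. Section 3.3.2 follows with "No follow up for withdrawn subjects", again without separating consent withdrawal from medical removal. Section 18.4 ends adverse event monitoring when a subject is withdrawn. These three sections agree with one another.

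Section 1.1 names five secondary outcomes to be compared between arms: blood parameters, VO2max, LVEF, quality of life, and "tumor response (tissue blocks from biopsy and surgical resection, MRI"). Section 8.3 specifies a mixed-model repeated measures analysis for VO2max, LVEF and MRI tumour response, and says "All efficacy outcomes will be assessed under the intention to treat principle". It gives no missing-data assumption. It names no model for blood parameters or quality of life.

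**The concern.** Only one of the five secondary outcomes, VO2max, needs an exercise test. A rule based on fitness to exercise therefore also discards later values of outcomes that could still be obtained, and it does so because of the woman's health. With 10 women per arm, each removal is 10% of an arm.

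At stake are the secondary comparisons and the completeness of the safety record. A likelihood-based mixed model can keep a removed woman through her earlier measurements. It is then valid only if, given what was observed, removal is unrelated to the values not observed. Section 3.2 contains the only list of contraindications, and it includes uncontrolled heart failure, symptomatic arrhythmia, myocarditis and pulmonary oedema. Several of these bear directly on cardiac function, so the assumption is hardest to defend for LVEF. Section 7.2.3 plans LVEF for all women only at baseline and after chemotherapy, so a woman removed in between may contribute nothing after baseline.

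**Working it through.** **1. The plan's own figure.** Section 8.2 takes "1.6 ± 0.35 L/min in the intervention group and 1.2 ± 0.23 L/min in the control group" and claims 80% power with 10 per group and unequal variances. The standard error is √(0.35²/10 + 0.23²/10) = √0.01754 = 0.132. The noncentrality is 0.4/0.132 = 3.02. The Welch test, two-sided at 0.05, gives 80.8%, so the claim reproduces. It makes no allowance for removals.

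**2. What could still be collected after a medical removal, with no new procedure.**

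| Outcome | Needs an exercise test? | Source | Obtainable? |
|---|---|---|---|
| VO2max | Yes (7.2.4) | Research test | No, once testing is contraindicated |
| LVEF, HER2-positive | No | Clinical echocardiograms during and after chemotherapy (7.2.3) | Yes |
| LVEF, HER2-negative | No | Post-chemotherapy echocardiogram is research only (7.2.3) | Only if done clinically |
| Laboratory values | No | Records checked every cycle (10.1, 10.2, 10.4) | Yes |
| Quality of life | No | Surveys sent through REDCap (18.2) | Yes |
| Surgical pathology | No | Resection tissue (1.1) | Yes |
| MRI | No | Named in 1.1 and 8.3, scheduled nowhere | Only if done clinically |
| Adverse events | No | Monitoring under 18.4 | Yes |

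**3. Size, under assumptions.** The documents give no removal rate, removal mechanism or baseline-final correlation. The simulation used 10 per arm, no true effect and 100,000 trials per scenario, with analysis of covariance on baseline among women with final values. Women were removed one after another with weight proportional to exp(−g × standardised final value). The settings were g = 0 (random), g = ln 1.6 or ln 2.7 (odds of removal rising 1.6-fold or 2.7-fold per SD lower), and always the lowest two as an upper end. Correlations of 0.5, 0.8 and 0.9 were tried.

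Bias for recoverable outcomes (equal SDs, two women removed from one arm), in SD units:

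| Removal | ρ = 0.5 | ρ = 0.8 | ρ = 0.9 |
|---|---|---|---|
| 1.6-fold | 0.073 | 0.036 | 0.019 |
| 2.7-fold | 0.135 | 0.068 | 0.037 |
| Lowest two | 0.245 | 0.126 | 0.069 |

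The estimate's own standard error runs from about 0.43 SD (ρ = 0.5) to 0.21 SD (ρ = 0.9). The largest graded bias is therefore 0.135/0.43, or about 0.31 standard errors. False positives are about 5% to 6.5% in the graded cases and about 6% to 10% at the upper end. If each arm loses two women by the same mechanism, the bias averages zero.

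VO2 (SDs 0.35 and 0.23), which the fix cannot recover:
- Two exercisers removed at random: bias about 0, false positives 6.3% to 6.5%. With no removal they are 5.3% to 5.5%. The increase comes from unequal SDs combined with unequal arm sizes, not from health-related removal.
- Two exercisers, graded: +0.007 to +0.047 L/min, which is 0.007/0.4 = 2% to 0.047/0.4 = 12% of the planning difference; false positives 6.5% to 8.4%.
- Two exercisers, lowest two: +0.025 to +0.089 L/min; false positives 8.3% to 14.0%.
- Two controls, graded: −0.004 to −0.032 L/min, so the sign reverses.

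**4. Safety test.** Sections 8.3 and 10.7 compare the proportion of patients with an event. The event that triggers removal should already be recorded. Only a woman whose first counted event comes after removal changes the test, by 1/10 = 10 percentage points in her arm. The documents do not allow an estimate of how often that would happen.

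**The case against.** The strongest reply is that this is a pilot. Section 1.2 makes study completion the primary endpoint, section 1.3 lists no secondary endpoints, and withdrawal is itself a feasibility result. The graded bias is small against sampling noise, losing two women from one arm only is an assumption, and the largest figures concern VO2, where nothing can be recovered. All of that stands, and it limits the weight of the point. It does not remove it: section 1.1 sets between-arm comparison as a secondary aim, section 8.3 plans two-sided tests for it, and the remedy is cheap.

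A reader might go further in four ways that the documents do not support.
- That the rule contradicts the intention-to-treat statement. It does not: section 18.3 places the baseline exercise test before randomisation, and a mixed model can keep every randomised woman in her assigned arm.
- That the trial will be biased in favour of exercise. Removal applies to both arms and the sign depends on which arm loses women.
- That the false-positive rate could reach 14%. This needs the two worst exercisers, and no controls, to be removed every time, for an outcome that the fix cannot rescue.
- That continued follow-up would restore all five outcomes. It would not restore VO2max after a testing contraindication, or LVEF in HER2-negative women without a clinical echocardiogram, and no section schedules an MRI.

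**Conclusion.** The point holds as a minor, inexpensive improvement. The text is clear: medical removal in either arm ends all follow-up, including of outcomes that need no exercise test. The missing-at-random assumption behind the mixed model for VO2max, LVEF and MRI is unstated and doubtful, most clearly for LVEF. No such assumption can be attributed to blood parameters or quality of life, because section 8.3 names no model for them; their loss is simply avoidable.

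The size and direction of bias cannot be derived from the documents. The range of 0.02 to 0.14 SD for recoverable outcomes rests on an assumed loss of two of 10 women from one arm, an assumed graded mechanism and an assumed correlation of 0.5 to 0.9. The VO2 figures support stating the assumption, not the extra follow-up. The feasibility endpoint is unaffected. Confidence is high in the gap in the text, but not in any material effect on this trial's results.

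**What to change.** In sections 3.3.1, 3.3.2 and 18.4, separate stopping exercise or exercise testing from leaving the study. Leave the clinical rule for stopping as it is.

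For women removed only for a medical contraindication, who retain capacity and have not withdrawn consent, continue adverse events, REDCap surveys, laboratory values and any clinically performed MRI or echocardiogram up to the planned final visit (before surgery, section 16.1). Add pathology from the later resection. Analyse these women as randomised.

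Do not extend this to women who withdraw consent or lose capacity. The contraindications in section 3.2 include "mental impairment leading to inability to cooperate", so a contraindication can itself mean loss of capacity; section 5.3.2.1 says of capability to consent, "This will be determined by the oncologist". Do not extend it either to the criterion that begins "Subject is imprisoned, committed to a mental hospital, hospitalized for long term care".

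In section 8.3, state the missing-at-random assumption for the outcomes in the mixed model, and report numbers and reasons missing by arm. Say that VO2max after a testing contraindication, and LVEF in HER2-negative women without a clinical echocardiogram, will remain missing. A simple sensitivity analysis that lowers the missing values is optional.

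The cost is protocol and consent wording, and a little staff time to abstract records and chase surveys for the few women removed. No new procedures are needed.

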4.0 Recruitment Methods

4.1 Identification of subjects

PSCI

Study staff will conduct an initial eligibility screening based on chart review to determine if the patient is eligible based on the following inclusion criteria: female, not pregnant, breast cancer diagnosis (Stage I-III C), no previous history of anthracycline use, absence of heart disease. If the patient is eligible the study staff will contact the treating oncologist for permission to approach the patient.

Andrews Patel

Similar to above, a research nurse will weekly screen whether there are new breast cancer patients scheduled to receive chemotherapy. Following identification of these patients, the research nurse will obtain physicians approval to approach patient.

4.2 Recruitment process

PSCI

Patients meeting initial eligibility criteria for this study will be contacted by study staff over the phone or in-person. Study staff will confirm the patient does not present with the following exclusion criteria: acute myocardial infarction, unstable angina, uncontrolled arrhythmias causing symptoms or hemodynamic compromise, syncope, acute endocarditis, acute myocarditis or pericarditis, uncontrolled heart failure, acute pulmonary embolus or pulmonary infarction, thrombosis of lower extremities, suspected dissecting aneurysm, uncontrolled asthma, pulmonary edema, room air desaturation at rest $\leq 85\%$, respiratory failure, acute non-cardiopulmonary disorder that may affect exercise performance or be aggravated by exercise, mental impairment leading to inability to cooperate. Study staff will then discuss the study in detail to make the patient aware of the procedures, intervention, and time commitment involved with the study.

Andrews Patel

If the medical oncologist gives clearance, the research nurse will approach the patient either by phone or in-person for presentation of the study. During this phone call / meeting, the nurse will briefly explain the trial, and will ask for permission to give contact details of the patient, and some clinical info to Penn State study staff. If the patient gives permission, study staff will contact the patient to provide more information about the study and confirm the additional eligibility questions (see phone script).

4.3 Recruitment materials

4.4 Eligibility/screening of subjects
See above.

5.0 Consent Process and Documentation

5.1 Consent Process

5.1.1 Obtaining Informed Consent

5.1.1.1 Timing and Location of Consent

PSCI and Andrews Patel: If the patient remains interested in the study after screening and recruitment, study staff will schedule a joint consent session and baseline visit at the exercise testing facility. This visit will be scheduled before or following another clinical visit in order to minimize visits to the institution. During the consent session we will answer any remaining questions and we will obtain written informed consent prior to any study activities.

5.1.1.2 Coercion or Undue Influence during Consent

While exercise is recommended during cancer treatment, women will be reminded that self-directed walking is also an available alternative for them.

5.1.2 Waiver or alteration of the informed consent requirement

Requested for screening/recruitment purposes only

5.2 Consent Documentation

5.2.1 Written Documentation of Consent

Written informed consent will be obtained prior to initiating any study related activities with the patient.

5.2.2 Waiver of Documentation of Consent

If a subject is interested in enrolling in the clinical trial (i.e. expresses interest to the clinician for the researchers to call her), this will be considered implied consent. Researchers will conduct the telephone script and schedule to meet with the subject to obtain formal written consent.

5.3 Consent – Other Considerations

5.3.1 Non-English Speaking Subjects

Study staff are not fluent in languages other than English.

5.3.2 Cognitively Impaired Adults

n/a

5.3.2.1 Capability of Providing Consent

This will be determined by the oncologist.

5.3.2.2 Adults Unable To Consent

A contraindication to exercise stress testing, and thus an ineligibility criteria is mental impairment leading to inability to cooperate.

5.3.2.3 Assent of Adults Unable to Consent

n/a

5.3.3 Subjects who are not yet adults (infants, children, teenagers)

5.3.3.1 Parental Permission

n/a

5.3.3.2 Assent of subjects who are not yet adults

n/a

6.0 HIPAA Research Authorization and/or Waiver or Alteration of Authorization

6.1 Authorization and/or Waiver or Alteration of Authorization for the Uses and Disclosures of PHI

Check all that apply:

- Not applicable, no identifiable protected health information (PHI) is accessed, used or disclosed in this study. *[Mark all parts of sections 6.2 and 6.3 as not applicable]*
- Authorization will be obtained and documented as part of the consent process. *[If this is the only box checked, mark sections 6.2 and 6.3 as not applicable]*
- Partial waiver is requested for recruitment purposes only (Check this box if patients' medical records will be accessed to determine eligibility before consent/authorization has been obtained). *[Complete all parts of sections 6.2 and 6.3]*
- Full waiver is requested for entire research study (e.g., medical record review studies). *[Complete all parts of sections 6.2 and 6.3]*
- Alteration is requested to waive requirement for written documentation of authorization (verbal authorization will be obtained). *[Complete all parts of sections 6.2 and 6.3]*

6.2

6.2.1 Access, use or disclosure of PHI representing no more than a minimal risk to the privacy of the individual

6.2.1.1 Plan to protect PHI from improper use or disclosure

Information is included in the "Confidentiality, Privacy and Data Management" section of this protocol.

6.2.1.2 Plan to destroy identifiers or a justification for retaining identifiers

We will identify eligible patients through electronic medical records prior to their consent in the study (pre-screen eligibility criteria). This information will be collected/retained on patients whom consent to be part of the study. No information from this screen will be collected/retained on patients whom do not consent to be part of the study.

6.2.2 Explanation for why the research could not practicably be conducted without access to and use of PHI

We will be conducting exercise testing and counseling (for those randomized to the intervention group) prior to starting chemotherapy. The timeline between recommendation for chemotherapy and initiation of chemotherapy is often short. Therefore, it is imperative we initiate recruitment for the study as soon as possible and thus schedule research visits on the same days as the patient comes to the Cancer Institute for testing related to their clinical treatment.

6.2.3 Explanation for why the research could not practicably be conducted without the waiver or alteration of authorization

Pre-screening individuals through electronic medical records allows for the timing of physician approval and approach of the patient. This study flow is being utilized to minimize patient burden for excess visits to the Cancer Institute for the research study.

